**Table 5-1: Observed ORR with Exact 95% CI in Platinum Eligible Subjects randomized to nivolumab plus ipilimumab (N=120)**

| Observed ORR | 95% Exact CI   |
|--------------|----------------|
| 10%          | (5.3%, 16.8%)  |
| 20%          | (13.3%, 28.3%) |
| 30%          | (22.0%, 39.0%) |
| 40%          | (31.2%, 49.3%) |

| Observed ORR | 95% Exact CI   |
|--------------|----------------|
| 50%          | (40.7%, 59.3%) |
| 55%          | (45.7%, 64.1%) |

About 60 subjects will be randomized to nivolumab plus ipilimumab placebo arm. The following table summarizes the 95% exact CI when observed ORRs are between 10% and 55% respectively.

**Table 5-2: Observed ORR with Exact 95% CI in Platinum Eligible Subjects randomized to nivolumab plus ipilimumab placebo (N=60)**

| Observed ORR | 95% Exact CI   |
|--------------|----------------|
| 10%          | (3.8%, 20.5%)  |
| 20%          | (10.8%, 32.3%) |
| 30%          | (18.8%, 43.2%) |
| 40%          | (27.6%, 53.5%) |
| 50%          | (36.8%, 63.2%) |
| 55%          | (41.6%, 67.9%) |

## 6 STUDY PERIODS, TREATMENT REGIMENS AND POPULATIONS FOR ANALYSES

### 6.1 Study Periods

#### 6.1.1 Baseline Period

Baseline evaluations or events will be defined as evaluations or events that occur before the date and time of the first dose of study treatment.

In cases where the time (onset time of event or evaluation time and dosing time) is missing or not collected, the following definitions will apply:

- Pre-treatment AEs will be defined as AEs with an onset date prior to but not including the day of the first dose of study treatment
- Baseline evaluations (laboratory tests, pulse oximetry and vital signs) will be defined as evaluations with a date on or prior to the day of first dose of study treatment

If there are multiple valid assessments, the assessment that is closest to day (and time if collected) of the first dose of study treatment will be used as the baseline in the analyses. If multiple assessments are collected at the same date (and time if collected), the assessment with the latest database entry date (and time if collected) will be considered as baseline.

#### 6.1.2 Post Baseline Period

On-treatment AEs will be defined as AEs with an onset date and time on or after the date and time of the first dose of study treatment (or with an onset date on or after the day of first dose of study

treatment if time is not collected or is missing). For subjects who are off study treatment, AEs will be counted as on-treatment if the event occurred within 30 days (or 100 days depending on analysis) (see Core Safety SAP), of the last dose of study treatment. No “subtracting rule” will be applied when an AE occurs both pre-treatment and post-treatment with the same preferred term and grade.

On-treatment evaluations (laboratory tests, pulse oximetry and vital signs) will be defined as evaluations taken after the day (and time, if collected and not missing) of first dose of study treatment. For subjects who are off study treatment, evaluation will be counted as on-treatment if it occurred within 30 days (or 100 days depending on analysis) of the last dose of study treatment.

## 6.2 Treatment Regimens

The treatment group “**as randomized**” will be retrieved from the IVRS system

Subjects will be randomized, in a 2:1 ratio, to one of the following treatment arms:

- Arm A: Nivo 3 mg/kg Q2W + Ipi 1 mg/kg Q6W
- Arm B: Nivo 3 mg/kg Q2W + Ipi Placebo Q6W

The treatment group “**as treated**” will be the same as the arm randomized by IVRS. However, if a subject received the incorrect treatment for **the entire period** of treatment, the subject’s treatment group will be defined as the incorrect treatment the subject actually received.

## 6.3 Populations for Analyses

- Enrolled subjects: All subjects who signed an informed consent form and were registered into the IVRS. This is the dataset for pre-treatment disposition.
- Randomized subjects: All enrolled subjects who were randomized to any treatment arm in the study. This is the primary dataset for analyses of study conduct, study population, and efficacy.
- Treated subjects: All randomized subjects who received at least one dose of study drug (nivolumab or ipilimumab). This is the primary dataset for analyses of exposure and safety.
- Response evaluable subjects: randomized subjects whose change in the sum of diameters of target lesions was assessed (i.e., target lesion measurements were made at baseline and at least one on-study visit.)
- PK subjects: All subjects treated with Nivolomab or ipilimumab with available serum time-concentration data.
- Biomarker subjects:
  - All tested PD-L1 subjects: All subjects who had a tumor biopsy specimen available for assessment of PD-L1 expression. [Note: This population is not just limited to randomized subjects since some screen failure subjects may have tumor biopsy specimens for PD-L1 testing]
  - All randomized subjects with quantifiable PD-L1 expression at baseline: See definitions of baseline and quantifiable PD-L1 expression in [Section 4.3.6](#).
  - All randomized subjects with quantifiable TMB at baseline.

- PRO Subjects: All randomized subjects with available Patient Reported Outcomes (PRO) data.
- Immunogenicity (ADA evaluable) subjects: Treated subjects with baseline and at least one post-baseline pre-infusion immunogenicity assessment. See Core/Integrated Statistical Analysis Plan for Immunogenicity

All analyses will be performed using the treatment arm as randomized (intent to treat), with the exception of dosing and safety, for which the treatment arm as received will be used.

## **7 STATISTICAL ANALYSES**

### **7.1 General Methods**

Unless otherwise noted, the bulleted titles in the following subsections describe tabulations of discrete variables, by the frequency and proportion of subjects falling into each category, grouped by treatment (with total). Percentages given in these tables will be rounded and, therefore, may not always sum to 100%. Continuous variables will be summarized by treatment group (with total) using descriptive statistics; ie, number of non-missing observations (n), mean, standard deviation (STD), median, minimum, maximum and quartiles. If a missing category is not being presented in the data display, only those subjects with non-missing values for the parameter being assessed are included in the percentage calculation.

Time to event distributions (i.e. progression free survival, overall survival, time to response, and duration of response) will be estimated using the Kaplan-Meier product limit method. When appropriate, estimates of the median time to event will be presented, along with associated 95% CIs. The confidence interval for the median will be obtained based on the log{-log} transformation of the survival function. Kaplan-Meier estimates of rates at fixed time points (e.g. OS at 12 months) will be presented along with 95% confidence intervals for those rates. The confidence interval for the rate at time  $t_0$ ,  $S(t_0)$ , will be obtained by first computing the interval for  $\log(-\log(S(t_0)))$  and then back transforming. (The methods specified above for computing the confidence intervals for median time to event and for survival rates are the default methods in SAS.)

Unless otherwise specified, the hazard ratio of Nivolumab plus ipilimumab to Nivolumab plus ipilimumab placebo, and its associated CI, will be obtained by fitting a stratified Cox model with the treatment group variable as the sole covariate using stratification factor recorded in the IVRS.

Confidence intervals for binomial proportions will be derived using the Clopper-Pearson method.

P-values from sensitivity analyses for efficacy endpoints are for descriptive purpose only and there will be no multiplicity adjustment for these analyses.

## **7.2 Study Conduct**

### **7.2.1 Accrual**

The accrual pattern will be summarized per country, investigational site, and per month for all enrolled and randomized subjects. Randomization date, first dosing date, country, investigational site will be presented in a by subject listing of accrual.

Furthermore, the accrual pattern will be summarized by the stratification factors for all randomized subjects alone.

### **7.2.2 Relevant Protocol Deviations**

The following programmable deviations will be considered as relevant protocol deviations and summarized by treatment group and total in all randomized subjects, overall and for platinum refractory and platinum eligible subgroups separately. Non-programmable relevant eligibility and on-treatment protocol deviations, as well as significant (both programmable and non-programmable) eligibility and on-treatment protocol deviations will be reported through ClinSIGHT listings.

#### Eligibility:

- Subjects without measurable disease at baseline.
- Subject with baseline ECOG PS > 1
- Subjects who received prior treatment with an anti-PD-1, anti-PD-L1, anti-CD137, anti-CTLA-4 antibody
- Any prior treatment with any non-platinum containing systemic therapy regimen for SCCHN (adjuvant, neoadjuvant, or multi-modal treatment)

#### On-study:

- Subjects receiving concurrent anti-cancer therapy (defined as chemotherapy, hormonal immunotherapy, radiation therapy directed to target lesions, surgery (surgical resection of tumor only), standard or investigational agents for treatment of SCCHN).
- Subject treated differently as randomized (subjects who received the wrong treatment, excluding the never treated).

Listings will also be provided.

## **7.3 Study Population**

Unless otherwise specified, analyses will be performed for all randomized subjects by treatment group as randomized, overall and for platinum refractory and platinum eligible subgroups separately.

### **7.3.1 Subject Disposition**

The total number of subjects enrolled (randomized or not randomized) will be presented along with the reason for not being randomized. This analysis will be performed on the All Enrolled Subjects population only.

Number of subjects randomized but not treated along with the reason will be tabulated by treatment group as randomized.

Number of subjects who discontinued study treatment along with corresponding reason will be tabulated by arm, as treated. Reason for discontinuation will be derived from subject status CRF page. This analysis will be restricted to the all treated subjects population.

A subject listing for all randomized subjects will be provided showing the subject's randomization date, first and last dosing date, off treatment date and reason for going off treatment. A subject listing for subjects not randomized will also be provided, showing the subject's race, gender, age, consent date and reason for not being randomized.

### **7.3.2 Demographics and Other Baseline Characteristics**

The following baseline characteristics (CRF source/clinical database) will be summarized by treatment arm as randomized:

- Age (descriptive statistics)
- Age categorization (<65 vs. ≥65)
- Age categorization (< 65, 65- <75, ≥ 75)
- Gender (Male vs. Female)
- Race (White, Black , Asian, Other)
- Ethnicity (Hispanic/Latino, Not Hispanic/Latino, Unknown)\*  
\* Required for US subjects only
- Country
- Region (North America vs. EU vs.ROW)
- Baseline ECOG performance status(0,1)
- Platinum-refractory (yes/no)
- HPV-16 status (Oropharyngeal HPV positive, HPV positive with unknown primary site, Oropharyngeal HPV negative, other site with HPV positive, other site with HPV negative, other site with no HPV result available)
- PD-L1 (expressing (≥1%), non-expressing (<1%), non-evaluable, indeterminate)
- Subjects with CNS metastasis at Baseline (Yes, No) - per radiographic tumor screening assessment
- Smoking status (former/current, never, unknown)
- Alcohol status (former, current, never, unknown)
- Tumor mutation burden (TMB)

Baseline Stratification Factors as entered into the IVRS will tabulated for all randomized subjects:

- PD-L1 status (expressing vs non-expressing/non-evaluable/indeterminate)
- HPV p-16 status (oropharyngeal HPV p16 positive (including unknow primary with HPV p16 positive) vs oropharyngeal HPV p16 negative or nonoropharyngeal)
- Platinum refractory subgroup (yes vs no).

### **7.3.3 Baseline Disease Characteristics**

The following baseline disease characteristics will be summarized.

- Disease stage at study entry (locally recurrent, locally recurrent and metastatic, metastatic)
- Disease stage at initial diagnosis (stage I, II, III, IVA, IVB, IVC)
- TMN Classification at initial diagnosis
- Time from Initial Disease Diagnosis to Randomization (< 1 year, 1 - < 2 year, 2 - < 3 year, 3 - < 4 year, 4 - < 5 year, ≥ 5 year).
- Sites of diseases (all lesions) per BICR
- Number of disease sites per subject (all lesions) per BICR
- Number of target lesions, non-target lesions and disease sites at baseline as per BICR
- Tumor burden: sum of the diameters of target lesions at baseline per BICR
- Sites of diseases (all lesions) per investigator
- Subsites of diseases per investigator

### **7.3.4 Prior Therapy**

#### Prior systemic anti-cancer therapy

Prior systemic anti-cancer therapy (which will be identified from the CRF page “Prior Systemic Therapy”) will be categorized using the BMS WHO drug dictionary and will be summarized overall and by treatment group. The latest version of the drug dictionary at the time of the analysis will be used. The number and percentage of subjects with any prior systemic anti-cancer therapy and the number of subjects receiving each therapy (generic term) will be presented.

- Prior systemic cancer therapy summary classified by setting, therapeutic class and generic name
- Best response to most recent prior systemic therapy regimen (CR, PR, SD, PD, Unable to determine, Not applicable, Not reported)
- Time from completion of most recent prior systemic therapy regimen to randomization (< 3 months, 3 - < 6 months, 6 - < 12 months, 12 - < 24 months, ≥ 24 months)\*

In addition, frequencies and percents will be provided for the following:

- Prior surgery related to cancer (yes, no, not reported) and reason for prior surgery
- Prior radiotherapy (yes, no, not reported) , reason for prior RT, total dose received
- Time from completion of most recent radiotherapy to randomization (< 3 months, 3 - 6 months, > 6 months)

\*The date of the last dose of platinum or the date of progression may be incomplete. If only the day is missing, it will be imputed as the 1st of the month. If either the month or the year is missing, the date will be considered missing.

#### Other prior therapy:

- Prior/current non-study medication classified by anatomic and therapeutic classes.

Agents and medication will be reported using the generic name. A listing by subject will also be provided.

### **7.3.5 Baseline Safety Laboratory Tests**

Baseline safety laboratory evaluations will be the latest available samples taken on or before Cycle 1, Day 1. Baseline safety laboratory values will be presented by CTC severity grade, by treatment group. These analyses will be restricted to treated subjects. Separate tables will be generated for hematology and Serum Chemistry.

CTC grades will be derived as part of the analysis data set programming using version 4.0.

### **7.3.6 Medical history**

General medical history will be tabulated and also listed by subject.

### **7.3.7 Baseline Examinations**

Subjects with abnormal baseline physical examination will be tabulated by examination criteria and by treatment arm.

### **7.3.8 Baseline Physical Examination**

Summary of baseline height and weight will be tabulated and presented.

### **7.3.9 Discrepancies Between IVRS and CRF stratification factors**

Summary tables (cross-tabulations) by treatment arm for each baseline stratification factor will be provided to show any discrepancies between what was reported through IVRS vs. CRF data/clinical database.

- PD-L1 status (expressing vs non-expressing/non-evaluable/indeterminate)
- HPV p-16 status (oropharyngeal HPV p16 positive (including unknow primary with HPV p16 positive) vs oropharyngeal HPV p16 negative or nonoropharyngeal)
- Platinum refractory subgroup (yes vs no).

## **7.4 Extent of Exposure**

Listings will include all available exposure data. Analyses will be performed by treatment group “as treated” in all treated subjects, overall and for platinum refractory and platinum eligible subgroups separately, unless otherwise specified.

### **7.4.1 Administration of Study Therapy**

The following parameters will be summarized (descriptive statistics) by treatment group, using all treated population.

- Time from randomization to first dose of study therapy ( $\leq 3$ , 4 - 5, 6-7, 8-14, 15 - 21,  $> 21$  to 28,  $>28$  days)
- Duration of treatment (in month) will be presented using a Kaplan-Meier curve whereby the last dose date will be the event date for those subjects who are off study therapy. Median

duration of treatment and associated 95% CI will be provided. Subjects who are still on study therapy will be censored on their last dose date.

- Relative dose intensity (%) by drug using the following categories: < 50%; 50 - < 70%; 70 - < 90%; 90 - < 110%; ≥ 110%.
- Number of doses received by drug (summary statistics).
- Cumulative dose by drug (summary statistics).

A by-subject listing of dosing of study medication (record of study medication, infusion details, and dose changes) and a listing of batch numbers will be also provided.

Table 7.4.1-1 below summarizes the key parameters used for analyses of dosing.

**Table 7.4.1-1: Administration of Study Therapy - Definition of Parameters**

|                              | Nivolumab  | Ipilimumab   |
|------------------------------|--|--|
| Dosing schedule per protocol | 3 mg/kg every 2 weeks  | 1 mg/kg every 6 weeks  |
| Dose                         | Dose (mg/kg) is defined as the minimum of [vial strength (mg/mL) *total volume infused (mL)] /most recent weight (kg) and nominal dose (mg/kg) * total volume infused (mL) /total volume prepared (mL) | Dose (mg/kg) is defined as the minimum of [vial strength (mg/mL) *total volume infused (mL)] /most recent weight (kg) and nominal dose (mg/kg) * total volume infused (mL) /total volume prepared (mL) |
| Cumulative Dose              | Cum dose (mg/kg) is sum of the doses (mg/kg) administered to a subject during the treatment period.  | Cum dose (mg/kg) is sum of the doses (mg/kg) administered to a subject during the treatment period.  |
| Relative dose intensity (%)  | $\text{Cum dose (mg/kg)} / [(\text{Last Nivo dose date} - \text{Start Nivo dose date} + 14) \times 3 / 14] \times 100$   | $\text{Cum dose (mg/kg)} / [(\text{Last Ipi dose date} - \text{Start Ipi dose date} + 42) \times 1 / 42] \times 100$   |
| Duration of treatment        | Last dose date - Start dose date +1  | Last dose date - Start dose date +1  |

Volume infused, volume prepared, and weight are collected on the CRF

## 7.4.2 Modifications of Study Therapy

### 7.4.2.1 Dose delays

For nivolumab, treatment may be delayed for up to a maximum of 6 weeks from the last dose. Subjects receiving nivolumab may be dosed no less than 12 days from the previous dose.

Each study medication infusion may be delayed independently. A dose will be considered as actually delayed if the delay is exceeding 3 days (i.e., greater than or equal to 4 days from scheduled dosing date) from previous dose for any given study medication. The length of delay for nivolumab is defined as (duration of previous cycle in days - 14). The length of delay for ipilimumab or ipilimumab-placebo is defined as (duration of previous cycle in days - 42). Dose delays for each study medication will be divided into following categories: on-time, 4 - 7 days, 8 - 14 days, 15 - 42, > 42 days. Reason for dose delay will be retrieved from the respective CRF

dosing pages for each study medication. If different reasons for delay are recorded (in the same cycle), both the reasons will be reported.

The following parameters will be summarized, by drug:

- Number of subjects with at least one dose delayed, number of doses delayed per subject, length of dose delay and Reason for dose delay

#### **7.4.2.2 Infusion Interruptions and Rate Changes**

The following parameters will be summarized from the CRF pages for all treatment drugs:

- Number of subjects with at least one dose infusion interruption, number of infusion interruptions per subject and the reason for interruption.
- Number of subjects with at least one IV infusion rate reduction, number of IV infusion rate reduction per subject and the reason for reduction

#### **7.4.2.3 Dose Reductions/Escalation**

Dose reduction/escalation is not permitted for nivolumab or ipilimumab or ipilimumab-placebo.

#### **7.4.3 Concomitant Medications**

Concomitant medications, defined as medications other than study medications which are taken at any time on-treatment (i.e. on or after the first day of study therapy and within 100 days following the last dose of study therapy), will be coded using the WHO Drug Dictionary.

The following summary tables will be provided:

- Concomitant medications (subjects with any concomitant medication, subjects by medication class and generic term).

A by-subject listing will accompany the table.

### **7.5 Efficacy**

Unless otherwise specified, efficacy analyses will be performed for all randomized subjects by treatment group as randomized, overall and for platinum refractory and platinum eligible subgroups separately.

CI's for efficacy endpoints will be at the two-sided 95% level, except for the primary endpoint ORR for platinum-refractory subjects where CI is anticipated to be provided at 98.5% level for the interim and 95.5% level for the final analysis (see [Section 7.5.1](#)). The p-values presented in the clinical study report will be rounded to the fourth decimal place. Point estimates and confidence intervals for efficacy variables will be rounded to the second decimal place. P-value will only be provided for the comparison of ORR between nivolumab in combination with ipilimumab vs nivolumab in combination with ipilimumab placebo in platinum refractory randomized subjects.

### 7.5.1 Primary Endpoint ORR in Platinum Refractory Subgroup

The primary endpoint of the study is ORR in platinum refractory subgroup, as determined by a blinded independent central review (BICR) using RECIST 1.1 criteria.

#### 7.5.1.1 Primary Analysis of ORR

The comparison of ORR between nivolumab in combination with ipilimumab vs nivolumab in combination with ipilimumab placebo in platinum refractory randomized subjects will be carried out using a two-sided Cochran-Mantel-Haenszel (CMH) test stratified by the stratification factors PD-L1 status (expressing vs non-expressing/non-evaluable/indeterminate) and HPV p-16 status (oropharyngeal HPV p16 positive (including unknown primary with HPV p16 positive) vs oropharyngeal HPV p16 negative or nonoropharyngeal) as recorded in the IVRS. The significance level will be adjusted for an interim analysis which will be performed when around 70% of platinum-refractory subjects have been followed for at least 6 months after randomization. Using Lan-DeMets alpha spending function with O'Brien-Fleming boundaries, the significance level for this comparison will be determined by the fraction of subjects included in the interim analysis. If the analysis is performed when exactly 70% of platinum refractory subjects have reached 6 months follow up after randomization, the alpha level is 0.015 for the interim and 0.045 for the final. An associated odds ratio (nivolumab/ipilimumab vs. nivolumab/ipilimumab placebo) and corresponding CI will be calculated. ORR will be summarized by a binomial response rate and its corresponding two-sided exact CI using Clopper-Pearson method for each treatment group. An estimate of the difference in ORRs between arms (nivolumab/ipilimumab vs. nivolumab/ipilimumab placebo) and corresponding CI will be calculated using Cochran-Mantel-Haenszel (CMH) methodology and adjusted by the stratification factors as recorded in the IVRS.

The formula is

$$\hat{\theta} = \frac{\sum_i w_i \hat{\theta}_i}{\sum_i w_i} \sim N \left[ \theta, \frac{\sum_i w_i^2 \left[ \frac{p_{ix}(1-p_{ix})}{n_{ix}-1} + \frac{p_{iy}(1-p_{iy})}{n_{iy}-1} \right]}{\left( \sum_i w_i \right)^2} \right]$$

where  $\hat{\theta} = p_{ix} - p_{iy}$  is the difference in rates in the *i*th stratum,  $w_i = \frac{n_{ix}n_{iy}}{n_{ix} + n_{iy}}$ , and  $n_{ix}$  and  $n_{iy}$  are the number of subjects randomized to treatments x and y, respectively, in the *i*th stratum.

BOR will be summarized by response category for each treatment group. The number and percentage of subjects in each category of best overall response (BOR) per BICR (complete response [CR], partial response [PR], stable disease [SD], progressive disease [PD], or unable to determine [UD]) will be presented, by treatment group.

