**Interim Analysis**

[figure not shown]

[figure not shown]
One interim analysis will be performed when around 70% of platinum-refractory subjects have been followed for at least 6 months after randomization. The comparison of ORR between nivolumab in combination with ipilimumab vs nivolumab in combination with ipilimumab placebo in platinum refractory randomized subjects will be carried out using a two-sided Cochran Mantel Haenszel (CMH) test stratified by the stratification factors as recorded in the IVRS. Using Lan DeMets alpha spending function with O'Brien-Fleming boundaries, the significance level for this comparison will be determined by the fraction of subjects included in the interim analysis. If the analysis is performed when exactly 70% of platinum refractory subjects have reached 6 months follow up after randomization, the alpha level is 0.015. Point estimate of ORR, and its corresponding two-sided 98.5% exact CI will be provided for each treatment group. The difference in ORRs between the two treatment groups and its corresponding 98.5% CI will be calculated using CMH methodology and adjusted by the stratification factors as recorded in the IVRS. The DOR, PFS and OS distribution will be estimated using Kaplan-Meier technique. Median survival time along with 95% CI will be provided for each treatment group. Similar descriptive analyses will also be performed for the platinum-eligible subgroups and both groups combined. Similar descriptive analyses may also be performed by HPV status, PD-L1, TMB, gene expression profiling, and other biomarkers in each subgroup alone or combined.

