## 4 ENDPOINTS

### 4.1 Primary Endpoint

#### 4.1.1 *Objective Response Rate by BICR and Duration of Objective Response in Platinum Refractory Subgroup*

Objective response rate by BICR and Duration of Objective Response (DOR) in the platinum refractory subgroup are the primary endpoints of this study. ORR is defined as the number of randomized subjects with a best overall response (BOR) of a complete response (CR) or partial

response (PR), assessed by BICR per RECIST 1.1, divided by the number of randomized subjects for each treatment group. Note that to achieve a best response of CR or PR, confirmation is required.

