## 5 SAMPLE SIZE AND POWER

The primary objective is to compare the ORR of nivolumab in combination with ipilimumab vs nivolumab in combination with ipilimumab placebo, as determined by BICR using Response Evaluation Criteria In Solid Tumors (RECIST 1.1) criteria in platinum refractory subjects with recurrent or metastatic SCCHN. The alpha level for the ORR is adjusted for one planned interim analysis using Lan-DeMets alpha spending function with O’Brien-Fleming boundaries, which will be determined by the fraction of subjects included in the interim analysis. Given that the interim analysis for the primary endpoint is expected to be performed when 70% of platinum refractory subjects have reached 6 months follow up after randomization, the alpha level is expected to be 0.015 for the interim analysis and 0.045 for the final analysis.

Approximately 396 subjects (216 platinum refractory subjects and 180 platinum eligible subjects) will be randomized to either nivolumab plus ipilimumab or nivolumab in combination with ipilimumab placebo in a 2:1 ratio.

A sample size of 216 randomized platinum refractory subjects (144 and 72 respectively) will provide 84% power for testing the odds ratio of nivolumab plus ipilimumab over Nivolumab in combination with placebo, with a 0.050 two-sided significance level, assuming ORR of 35% and 15% (odds ratio of 3.051) in the nivolumab plus ipilimumab and nivolumab in combination with ipilimumab placebo treatment group respectively (odds ratio of proportions test using EAST v6).

Only the primary endpoint will be tested, none of the secondary endpoints.

The first secondary objective is to estimate the ORR of the treatment of nivolumab in combination with ipilimumab vs nivolumab in combination with ipilimumab placebo, as determined by BICR using RECIST 1.1 criteria for first line treatment of recurrent or metastatic SCCHN in the platinum eligible setting.

Approximately 180 subjects (120 and 60 respectively) will be randomized in the platinum eligible subgroup. For a sample size of 120 subjects randomized to nivolumab plus ipilimumab, the maximum width of the exact two-sided 95% confidence interval (CI) is 18.6% when the ORR is expected to be in the 10% to 55% range. The table below summarizes the 95% exact CI when observed ORRs are between 10% and 55% respectively.

Table 5-1: Observed ORR with Exact 95% CI in Platinum Eligible Subjects randomized to nivolumab plus ipilimumab (N=120).

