#### **7.5.6 Interim Analysis**

One interim analysis will be performed when around 70% of platinum-refractory subjects have been followed for at least 6 months after randomization. The comparison of ORR between nivolumab in combination with ipilimumab vs nivolumab in combination with ipilimumab placebo in platinum refractory randomized subjects will be carried out using a two-sided Cochran-Mantel-Haenszel (CMH) test stratified by the stratification factors as recorded in the IVRS. Using Lan-

DeMets alpha spending function with O'Brien-Fleming boundaries, the significance level for this comparison will be determined by the fraction of subjects included in the interim analysis. If the analysis is performed when exactly 70% of platinum refractory subjects have reached 6 months follow up after randomization, the alpha level is 0.015. Point estimate of ORR, and its corresponding two-sided 98.5% exact CI will be provided for each treatment group. The difference in ORRs between the two treatment groups and its corresponding 98.5% CI will be calculated using CMH methodology and adjusted by the stratification factors as recorded in the IVRS.

The following sensitivity analyses may be conducted using the primary definition of ORR in platinum-refractory subjects:

- If one stratification variable at IVRS and at baseline (CRF and clinical database) disagrees for at least 10% of the randomized subjects, similar analysis of ORR will be performed using the strata as determined at baseline.
- ORR per BICR for subjects with no relevant deviation. This analysis will be conducted only if there are more than 5% subjects with relevant protocol deviations.

The DOR distribution will be estimated using Kaplan-Meier technique. Median survival time along with 95% CI will be provided for each treatment group.

The PFS and OS distribution will also be estimated using Kaplan-Meier technique. Median survival time along with 95% CI will be provided for each treatment group. The hazard ratio and the 95% confidence interval will be estimated in a stratified Cox proportional hazards model using the randomized arm as a single covariate, stratified by PD-L1 status and HPV p-16 status.

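### Does the plan leave open which platinum-refractory subjects enter the interim ORR test?

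*SAP*

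**What the plan says.** The protocol synopsis sets the trigger: "One interim analysis will be performed when around 70% of platinum-refractory subjects have been followed for at least 6 months after randomization". SAP 7.5.1.1 gives the level for the test under Lan-DeMets spending with O'Brien-Fleming boundaries: "the significance level for this comparison will be determined by the fraction of subjects included in the interim analysis". The next sentence is a worked example: "when exactly 70% of platinum refractory subjects have reached 6 months follow up after randomization, the alpha level is 0.015". The matching level at the final analysis is given as 0.045. Protocol 8.4.2.1 has the same two sentences in the same order. SAP 5 describes the adjusted alpha in the same way, "which will be determined by the fraction of subjects included in the interim analysis", and links the 70% trigger to the same two levels.

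The remaining relevant text is general. SAP 4.1.1 defines ORR as the number of responders "divided by the number of randomized subjects for each treatment group". SAP 7.5 says that, unless otherwise specified, "efficacy analyses will be performed for all randomized subjects by treatment group as randomized". The stratum counts in the formula for the difference in SAP 7.5.1.1 "are the number of subjects randomized to treatments x and y, respectively". SAP 7.5.6 says that the interim comparison "in platinum refractory randomized subjects will be carried out" with a stratified CMH test, and gives no follow-up limit. SAP 6.3 lists no separate interim population. The body of protocol 8.5, the interim section, is not visible in the public version.

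**The concern.** The alpha rule depends on who is included in the interim, yet no visible sentence says that only subjects with six months of follow-up are included. Someone who started from the ORR denominator and the all-randomized default could put every platinum-refractory subject randomized by the cut-off into the test. Confirmation of response is required, so many late entrants would count as non-responders only because their follow-up is short.

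This is the only interim look at the only endpoint that is formally tested, and the sponsor is blinded only until then. If the set were really open, two programmers could reach different interim verdicts and show different response rates. A choice made after unblinding could in principle also affect type I error.

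**Working it through.** **Inputs.** Two-sided alpha 0.05; 216 platinum-refractory subjects (144 and 72); ORR 35% vs 15%; levels 0.015 and 0.045 at 70% (SAP 5 and 7.5.1.1). Accrual of about 13 months (protocol 3.2), a whole-study figure. Uniform accrual is an assumption.

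**Step 1: reproduce the stated levels.** For O'Brien-Fleming-type spending, with one-sided 0.025 doubled, the alpha spent at fraction t is 4 × [1 − Φ(z₀.₉₈₇₅/√t)]. The final level is solved from the bivariate normal with correlation √t.

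| t | interim level | final level |
|---|---|---|
| 0.65 | 0.0109 | 0.0466 |
| 0.70 | 0.0148 | 0.0455 |
| 0.75 | 0.0193 | 0.0442 |

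The row for 0.70 matches the plan's 0.015; the final 0.045 is slightly conservative. Putting two-sided 0.05 directly into the function gives 0.0192 and 0.0430, which does not match. The subjects counted are therefore 0.70 × 216 = 151.2, or about 151: those with six months of follow-up.

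**Step 2: apply the same rule to everyone randomized.** With accrual over A months, 70% reach six months of follow-up at 0.7A + 6. The share of the 216 randomized by then is (0.7A + 6)/A, capped at 1.

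- A = 13: 0.7 × 13 + 6 = 15.1 months, after enrolment has closed. All 216 are in, 216 − 151 = 65 of them with under six months. The fraction is 1.00 and the interim level is 0.05.
- A = 24: 22.8/24 = 0.95, or 205 subjects, 54 with under six months. Levels 0.0429 and 0.0392.
- A = 30: 27/30 = 0.90, or 194 subjects. Levels 0.0363 and 0.0401.

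The fraction is 1.00 for any A up to 20 months. None of these levels is 0.015, and at 13 months the interim would use up all the alpha. The all-randomized reading therefore contradicts the example beside the rule.

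**Step 3: read the general wording in that light.** Dividing by the number randomized, analysing as randomized and weighting by numbers randomized are intention-to-treat statements. They rule out denominators of treated or response-evaluable subjects. The 151 are also randomized platinum-refractory subjects, so these statements hold within that set. The SAP 7.5 default gives way where something else is specified, and the interim rule with its example does specify.

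**Step 4: what if someone tested all randomized subjects at 0.015 anyway?** This mixes one reading's set with the other's alpha, so the plan's rule does not lead to it. It does show the scale. The simulation used 144 vs 72, uniform accrual over 13, 18 or 24 months and the cut six months after the 151st subject. First responses fell at weeks 6 to 24 in three assumed patterns, confirmed six weeks later. Tests were an unstratified z test and a CMH test over four strata (assumed 55% PD-L1 expressing, 25% HPV positive), at levels 0.015 and 0.045.

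| | the 151 | all randomized |
|---|---|---|
| chance of crossing at the interim, 35% vs 15% | 55-58% | 60-68% (13 months), 57-63% (18-24 months) |
| mean interim ORR | 34-35% vs 15% | 27-31% vs 12-13% |
| type I error, CMH, 28.3% in both arms | 4.90-5.08% | 4.54-4.84% |

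With the CMH test, interim verdicts differ in 13.6-18.1% of trials (13 months) or 10.1-14.6% (18-24 months). The overall verdict, interim or final, differs in 0.24-0.44% at 35% vs 15%, and in 0.8-1.0% at 25% vs 15% (z test only). Picking the better set after unblinding gives a type I error of 4.96-5.20%, with simulation error of about 0.1 point.

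**The case for a change.** The best case for acting is that an SAP should be self-sufficient, and this one leaves the interim set to inference. The example implies the 151, but the ORR definition, the efficacy default and the formula printed in the same section all speak of randomized subjects without a follow-up limit. If an analyst took the all-randomized set and kept 0.015, up to about one trial in six could get a different interim verdict, with visibly diluted response rates. A couple of sentences would settle it and need no new data.

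Part of this stands. The set is not named in so many words, and the displayed interim ORRs would differ between the sets. The one-in-six figure, though, compares two overlapping samples at the same strict threshold; it does not measure an ambiguity in the rule. Under the rule, a change of set moves the alpha as well, and Step 2 shows that this breaks the design. Fixing the set before unblinding would add little: under either reading it follows from randomization dates and the data cut-off, and SAP 2.3 keeps the sponsor blinded until the planned interim. Protocol 8.5 may already contain the missing sentence.

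**Conclusion.** This is a gap in wording that an analyst fills correctly from the adjacent example. The stated levels are right for a fraction of 0.70, and only the set with six months of follow-up, about 151 of 216, agrees with both the rule and those levels. Departing from that set while keeping 0.015 and 0.045 would make the test slightly conservative and would leave the final conclusion almost untouched. Naming the set would make the text easier to read but would alter no decision that the plan now leads to.

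The match of levels to fraction needs no assumption beyond the usual form of the spending function. The fractions for all randomized subjects assume uniform accrual and apply the whole-study 13 months to the subgroup, with 24 and 30 months as alternatives. The simulated percentages also depend on the assumed response timing and stratum shares. No change to the plan follows.
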